## 2. 1) Definition of KC

What is kangaroo care?

It is a special method of caring for a premature infant in which the baby is positioned for at least 1 hour a day in an upright skin-to-skin and chest-to-chest contact with its mother. This is started by moms in the NICU and continues at home for the first three months.

Ludington-Hoe, et al., (1990;2013&2018)

## 3. State the benefits of kangaroo care to infant-mother dyads.

Why should I perform Kangaroo Care?

Babies and mothers get a lot of benefits:

*3.1 For infants;*

- i) Increases the sleep of infants, which can enhance weight and brain development.
- ii) Controls temperature, heart rate, and respiration for infants.
- iii) Supports successful breastfeeding sessions and reduces infection.
- iv) Shortens the length of hospital stay.

*3.2 For mothers;*

- i) Increases confidence in ability to care for babies.
- ii) Enhances bonding, feeling of closeness with babies.
- iii) Improves mothers' milk production.
- iv) Creates more nurturing interactions.

4) Explain the kangaroo care technique.

*Who can perform Kangaroo Care?*

Mums should do it. Every medical situation at NICU, however, is different. So ask your nurse, if your infant is a successful candidate indeed. If you can't do KC or don't feel confident, don't worry. But there are plenty of ways to help and take care of your infant. Speak to your nurse.

*When can I perform Kangaroo Care?*

You can perform at any time between 90 to 120 minutes after feeding. Schedule a suitable time with your nurse and set aside at least 1 hour or 60 minutes a day, and plan to sit 4 to 5 hours a week with your baby. Please feel free to ask a member of the NICU team for further information.

5) State the preparation before, during and after the KC procedure.

*How do I perform Kangaroo Care?*

You're going to dress your baby up in a diaper and head cap. Your baby should be positioned upright between your breasts. Have its tummy against

your chest. Head turned to one side, arms and legs in a bent position.

Support your baby's head, back and buttocks. [Please refer to Appendix O (a) and O(b)].

Ludington-Hoe,et al.(1990,2013,2018) & Nqyist,(2010)

## **ii) Contents module for the practical session (30 minutes)**

### **Objective**

1. Reinforce mothers with proper hand-washing techniques. Wash hands each time when entering and leaving NICU, after diaper changes, personal hygiene and feeds. (Appendix N)

#### *How do I wash my hands correctly?*

Using the steps below, washing your hands properly requires about as long as you sing Happy Birthday twice.

- Wet hands with water
- Apply enough soap to cover all hand surfaces
- Rub hands palm to palm
- Right palm over left dorsum with interlaced fingers and vice versa.
- Palm to palm with fingers interlaced.
- Back of fingers to opposing palms with fingers interlocked
- Rotational rubbing of left thumb clasped in right palm and vice versa
- Rotational rubbing backwards and forwards with clasped fingers of the right hand in left palm and vice versa
- Rinse hands with water
- Dry through with a single-use towel

- Use a towel to turn off the faucet
- And your hands are safe.

(WHO,2020)

2. List the equipment for kangaroo care procedure;

### 2.1 Infant

- Infant thermometer
- Woollen head cap & woollen booties
- Diaper & receiving baby napkin
- Baby blanket

### 2.2 Mother

- Chair
- Blouse open in front
- Small mirror

3. Demonstrate and return-demonstrate

[figure not shown]

Figure 3.1: Shows the kangaroo care position

a) Greet mother, introduce yourself, and explain the purpose of the procedure.

Rational(R): Mother understands the correct KC position for the infant;(head midline, well flexed, nares/mouth visible)

b) Prepare the mother's and infant's equipment & screen mother and infant for

privacy.

R: Mother is comfortable and able to sit for a minimum of 60 minutes per day.

The mother should remove the bra and wear a blouse or robe that opens in front or tube. The mother eliminates the need to disrupt the KC session bowels opened (BO) and passed urine (PU).

c) Position the KC chair at the side of the incubator door.

R: To prevent unnecessary tension on the lines during transfer.

d) Assist the mother to sit on the chair next to the incubator with her blouse/shirt open or robe.

R: Ready to receive the infant for KC and ensure the entire body over the naked chest and abdomen is covered.

e) Monitor infant vital signs, such as temperature, respiration and heart rate; 15-30 minutes before and after KC.

R: To monitor baseline temperature, respiration and heart rate.

f) Place the infant in the supine position with receiving napkin/blanket underneath the head and torso / back of the infant.

R: To avoid heat loss.

g) Take off the infant's clothes and dress the infant in a diaper and head cap only.

R: To check if BO or PU and prepare for KC.

h) Cover the ends of the blanket to cover arms, legs, intravenous (IV) lines, and lead wires around the infant.

R: To prevent heat loss and dislodging all the lines.

i) Pick up the infant with the hand under head and buttocks close to your chest.

R: To support and stabilize the infant during transfer.

j) Place the infant prone on the chest of the mother, and pull the ends of the blanket

over.

R: To assure proper chest-to-chest; skin to skin contact.

k) Assure proper, safe positioning of the infant; head midline, neck straight, nares and mouth visible, arms and legs in a bent position.

R: To get the advantages of the KC effect.

l) Instruct mother to fold her arm across infant's back (non-dominant hand) and buttocks (dominant hand)

R: To prevent slipping down from her chest.

m) Place an additional folded blanket or wrap across the infant's back. Advise mother to cover her body or wear the blouse open in front (button) on top of the premature infant.

R: To keep baby warm.

n) Advise mother to be in KC position not less than 1 hour. Accumulatively continue KC for 4 to 5 hours a week and until the infant is 3 months old.

R: To complete the cycle of sleep.

o) Help the mother to initiate breastfeeding after the baby shows readiness and signs of feeding cues; moving tongue and mouth, licking the mother's skin during KC procedure.

R: To encourage partial or exclusive breastfeeding.

p) Tidy up the mother and equipment.

R: For comfort and cleanliness.

(United States Institute of Kangaroo Care, 2018)

4. *Documentation in kangaroo care record progress (KCPR) booklet.*

- Record the date, time, temperature, duration from time KC commences until

completion of the session, weight gain, and type of feeding intake daily in the KCRP booklet provided.

R: To monitor the frequency of KC, weight gain, and breastfeeding rates.

### **3.12 The process of delivery and how and who to conduct the KC-EP**

Face-to-face or direct contact is the best adult teaching method for nursing care, as there is no research available to determine whether different modes of delivery can produce better outcomes (Aranda, 2008). The delivery mode will determine how the intervention is exposed, the different methods used and the magnitude of the intervention in spite of similar intervention material. In this research, face-to-face or interpersonal communication has been identified as the delivery method for the KC-EP post-literature review.

Throughout their premature infant's hospitalization in the NICU, preterm infant mothers may face uncertainty about the progress of their preterm infant but may wait and rely on the knowledge, support, and advice of health professionals (Tandberg, Bente Silnes, Sandtø, Hege Pettersen, Vardal, Mari, Ronnestad & Arild, 2013). Good communication skills, such as integrity, respect, and practice of two-way communication, are key points for effective clinical interaction (Reid et al 2007). Subsequently, in order to ensure that mothers benefit from communication, all verbal details and knowledge communicated should be replicated and validated in written notes, as mothers under stressful conditions may not recall all information provided (Lee, Wang, Lin, Kao, 2013). Empowerment has been described as a nurturing mechanism that improves well-being through increased maternal knowledge, awareness, and skills, and reduces difficulties (Lee et al., 2013, Liu, Chao, Huang, Wei, & Chien, 2010). With the knowledge obtained, mothers will be confidently involved in taking care of their preterm infants in the NICU, which may enhance mother-infant dyad bonding, and reduce stress and anxiety among mothers (Liu et al., 2010). The above paragraph addresses the delivery method of KC-EP and the use of the empowerment concept

(partnership, participation, and collaboration) in implementing KC-EP. The researchers provided educational information and suggested that, with the kangaroo care strategy, mothers should care for their premature infants. The participation and cooperation of mothers was stepped up from time to time through meetings (first meeting and follow-up) and conversations between mothers and researchers in the WhatsApp group (face to face and one to one). The mothers were encouraged to ask and answer any questions or problems during meetings or telephone conversations, but the confidentiality of the contact was still maintained.

### **3.13 When, Where and How Much Will KC-EP be Delivered**

The question "When" refers to the timing, in particular the best time for the intervention program to be implemented and the question "How much" refers to the intervention's intensity in terms of the amount, duration and period of time needed to implement the intervention (Feeley, Nancy, Zelkowitz, Phyllis, Shrier, Ian, 2011). Timing and strength are two important aspects to be considered in the implementation of a nursing intervention. The duration and strength of the KC-EP implementation were agreed upon after analysis of literature review findings regarding mothers who were slightly more depressed at the beginning of enrolment. In the first week, the mothers were less stressed (Tandberg et al., 2013), and in the week after birth and the week after discharge, the mothers were most stressed and worried (Gennaro, York, & Brooten, 1990).

In this study, 48 hours after the admission of the premature infant to the NICU, or after the clinical stabilization of the infant, the expected intervention program was started, and the mother was able to perform KC. Within 48 hours post-admission, a specific orientation (reinforcement) and the first meeting were conducted. The second set of data was collected at the premature infant's age of 1 month (44 weeks). The duration and frequency of KC-EP

implementation were based on the guidelines (USIKC, 2018). Moreover, the Guidelines on Kangaroo Care, which was published by WHO (2003), was derived from Davanzo, Brovedani, Travani, Kennedy, Crocetta, Sanesi, Strajn., & De Cunto (2013). The duration or frequency of KC-EP implementation was also based on the Bakermans-Kranenburg, Van IJzendoorn, and Juffer (2003) studies. Meta-analysis results from Bakermans-Kranenburg et al. (2003) found that the most effective intervention consisted of less than 16 sessions, and that less than 5 sessions ( $d=0.33$ ) were as effective as a 5-16 session intervention ( $d=0.36$ ). Accordingly, after consideration of these findings by Bakermans-Kranenburg et al. (2003) the expert panel decided in this study to limit the number of sessions to the minimum possible in practice.

The KC-EP's design for mothers was based on the above discussion and consisted of two (2) sessions (first meeting and subsequent meeting), ten (10) short messages and reminder updates, and three (3) telephone follow-ups, and the program started immediately within 24 to 48 hours of admission. The sessions included an overview or welcoming meeting with the mother during the admission of her premature baby to the NICU (10 to 15 minutes), followed by two more meetings (first 60-minute meeting and subsequent 15 to 20-minute meeting).

### **3.14 Intervention**

Phase III required KC-EP intervention with premature infant mothers. During the admission, the researcher obtained demographic data and scheduled the KC-EP sessions. The researcher carried out the implementation to ensure consistency and equity in the delivery of KC-EP; this would allow the researcher to understand better the problems or difficulties of the mothers. The study appointed one senior staff nurse (working office hours) to assist the researcher to arrange the intervention process for the benefit of implementation.

#### **3.14.1 Meeting Place for the KC-EP Activities**

The conference room was chosen as it was quiet, and away from the noisy NICU environment. The mothers were never left alone during the answering session, where the researcher would always be available to offer the mothers some assistance. Sometimes the meeting place was also contingent on the condition of the mother. If the mother preferred to have the meeting elsewhere, alternate locations could be used, such as the breastfeeding room. If the mothers were able to carry out kangaroo care, the meeting would be held in the room arranged for them.

Mothers of premature infants admitted to the NICU face challenges, such as difficulties in accessing information regarding premature infant complications, and lack of experience in caring for their premature infants (Charchuk & Simpson, 2005). Therefore, in the current KC-EP, the senior staff nurse in charge was given the responsibility of explaining the aim of the intervention program to the mothers during their first visit, developing a supporting relationship with and showing concern for the mother, answering any simple questions asked by the mother and choosing an appropriate time for the intervention session based on the timetables (Appendix L&M). The average time for the mother's first visit to the NICU was between 1 and 3 hours depending on the conditions of any complications and the date of delivery. If the mother underwent a lower segment caesarean surgery it would take longer. In this study, the mothers' baseline data were collected within 48 hours of admission to give the mothers time to settle down and adapt to the new situation. The KC-EP maternal care time schedule, the mothers, premature infants and instruments used are shown in Table 3.2 (a) & (b).

### **3.14.2 The First Meeting**

In the first meeting, which was held within 48 hours of NICU admission, information was given to the mothers about preterm infants admitted to the NICU as well as the KC technique

to ensure they had knowledge of KC during 30 minutes of theory and 30 minutes of practical session. Based on the established KC-EP, the researcher went through the educational information. During this meeting, the researcher and the mother discussed openly any concerns or issues faced with regard to the implementation of KC and breastfeeding status. Any questions from the mother were answered accordingly. The mother was taught about the KC technique in theory and how to practice KC-EP based KC in order to develop her maternal responsibilities, knowledge, and skills in caring for her premature infant. The researcher gave the KCRP booklet to the mother and went through it with her to emphasize the booklet's importance. The researcher also sent reminders to the mother through WhatsApp in the form of short notes to ensure that the mother read and understood from time to time the prepared booklet. Meanwhile, the mother was asked to remind the nurse in charge of her next visit (reconfirmation of the date of the following meeting) so that the researcher could plan accordingly.

### **3.14.3 The Kangaroo Care Progress Record (KCPR) booklet.**

The creation of this booklet was based on the results of Phase I and adapted from the original article by Singh, Amritanshu, & Mukherjee (2014) and Biswas, Malpani & Ekka (2016) to fulfill the study's objectives. This was to ensure that the booklet for KCRP was suitable for mothers in the local context. The KCPR booklet was prepared in English and Malay language, with a table for date, time, length of KC, weight gain, and mode of breastfeeding. It also helped the mothers to gain information about the KC technique and its benefits. This KCPR booklet provided a motivational resource, particularly for mothers who were unable to visit the NICU on a daily basis and who were thus able to prepare for their next visit to provide KC for their premature infant so as to maximize KC implementation to between four (4) to five (5) hours in a week. The following information was included in the KCPR booklet.

In addition, premature infant mothers need to learn about the KC technique, the effects of KC, the average implementation of hours of KC per day, the devices used by the premature infant for the kangaroo care technique, premature infant growth, and premature infant nutrition up to the first 3 months. The KCPR booklet was limited to 30 pages in order to avoid information overload. Upon amendment, consent was given by all meeting committees, which consisted of two (2) senior nursing lecturers, one (1) matron in charge of the department and one (1) sister. The KC-EP for the mothers in the experimental group and the KCPR booklet were then sent to one neonatologist and one matron in charge of verification. The neonatologist and the matron in charge were invited to ensure that the module contents designed were compatible with the clinical and institutional needs. The KC-EP developed for mothers and the KCPR booklet were then given to four (4) mothers whose preterm infants were admitted to the NICU and five (5) NICU nurses who were not directly involved in the development of the KC-EP in order to verify the readiness of the KCPR booklet. There were no major issues raised by the two neonatologists and the matrons. The evaluation results showed that the evaluators, the four (4) mothers and five (5) nurses, could understand the contents of the KCPR booklet.

#### **3.14.4 Subsequent Meeting**

A subsequent meeting of 15 to 30 minutes was conducted on the 4th day of admission depending on the condition, willingness, and tolerance of the mother. The goal of the subsequent meeting or bedside teaching was to improve the therapeutic relationship between the mother and the researcher which had been established at the time of admission and to recognize any problems faced by the mother in performing the technique of KC. The interaction between the researcher and the mother was aimed at improving the mother's well-being. The strong interactions between the nurses (professional) and the mothers enhanced the mothers' knowledge, particularly on issues related to the KC technique and their infant's

admission to NICU. During the meetings, the mother was allowed to ask about and discuss any concerns or issues via telephone or WhatsApp conversation. Throughout the KC-EP activities, the researchers demonstrated a caring attitude, were knowledgeable about issues related to premature infant admission to the NICU, and had good listening skills. The meeting also highlighted and discussed the information found during Phase III.

### **3.14.5 Telephone call and short message via WhatsApp.**

To ensure continuity of the KC technique and quality of premature infant care, the researchers performed a follow-up through WhatsApp, sending a short message to the mother. This was a reminder about providing updates on the premature infant's performance of KC, the condition of the premature infant; i.e. body weight of preterm infant on discharge, at 1 month and 3 months corrected age, breastfeeding status every 2 weeks post-admission until 40 weeks post-admission. In addition, this continued every 4 weeks at 44 weeks, 48 weeks and 52 weeks of premature infant age [Table 3.2(a) & (b)]. The researchers also made three (3) telephone calls via WhatsApp during the program of which the first call was at 40 weeks post-admission, the second call was at 44 weeks (1 month) post-admission and the last call was at 52 weeks (3 months) post-admission. The purpose of the call was to find out if the mother had any doubts or had any problems linked to the objectives of the study at home and to advise the mother to contact the researcher at any time if she had any problems with KC and her premature infant's condition. All of the conversations were conducted using a very careful approach to ensure that the mothers were openly sharing their feelings and their appreciation of KC.

The program aimed to educate mothers on how to carry out KC and reduce their stress levels and how to strengthen their ability to breastfeed their premature infants. The nurses' workload in the NICU is generally very high, and nurses do not have enough time to assist

the mothers. Therefore, the entire program was allocated only 1 hour and 30 minutes. The experimental group had four sessions prepared and designed for the mothers, the specifics are set out in Appendix L and M. The program was administered in one session with between two (2) or four (4) mothers per group and one or two nurses involved at the first meeting. This was to ensure the nurses and mothers were given the same information , skills and shared attitudes.

The refresher meeting on how to give psychological support to the mothers on handwashing, KC, breastfeeding education, briefing on the KCPR booklet and the KC-EP was conducted by the researcher. The implementation of KC and the purposes of all the questionnaires were carefully explained during the meeting. Through this training, the nurses would get a clearer understanding of the intervention and the value of reporting in the KCPR booklet. Nonetheless, one of the senior nurses working office hours was not directly involved in the implementation of the KC-EP; she was responsible for tracking any new admission that met the study criteria, accurately recording the demographic data of the mother and premature infant, informing the researcher about any new admission, scheduling and verifying the date of the first meeting (48 hours post-admission), notifying the researcher on every new admission and collecting the post-intervention data on discharge (body weight, weeks and date of discharge). It was the responsibility of the researcher to assure that the KC-EP was appropriate and given equally to all mothers, and to collect the data at the first meeting.

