### 3.7.2 Sample Size Calculation for Mother-Infant Dyads

The sample size for mother-infant dyads was calculated using the two-sample independent t-test. This was based on a previous study and this study's primary outcome (Rao, Udani, & Nanavati, 2006). The two-tailed comparison group was used in the sample size calculation using the formula below. The mean difference in weight gain was 8.41 (Rao et. al., 2006) pre and post-intervention, while 0.8 was the standard deviation. These values were applied in the formula based on the study done by Rao et., al (2006).

$$\text{The formula, } n = \frac{2[Z\alpha/2 + Z\beta]^2 S^2}{(\mu_1 - \mu_2)^2}$$

$$\text{Thus, } Z\alpha/2 = 1.96 \quad Z\beta = 0.842$$

$$\mu_1 - \mu_2 = 0.54 \quad S = 0.8$$

$$\text{The formula, } n = \frac{2[1.96 + 0.84]^2 [0.8]^2}{(0.54)^2}$$

$$n = \frac{2 [ 2.802 ]^2 (0.64)}{0.29}$$

$$n = \frac{2 [ 7.85 ] (0.64)}{0.29}$$

$$n = \frac{10.05}{0.29}$$

Thus,  $n = 34.65 = 35$  subjects for each group.

Additional 30% = 50 subjects for each group.

An additional 30% was added to the estimated sample size to account for possible missing values and non- responses. The final sample size calculated was 50 for the sample population, and 50 for the experimental group.

The two groups of preterm infant-mothers were recruited from those who were admitted to the NICU. The first set of samples ( n=50) was recruited from early February 2018 until July 2018. The preterm infant-mother dyads who were admitted within these months were allocated to the control group, while recruitment for the experimental group of preterm infant-mother dyads (n=48) was initiated from early September 2018 until April 2019, after completion of the intervention program for the nurses. In both groups, the sample size for the control group was (n=48) and the experimental group (n=48), for a total sample size of (n=96).

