**Table 3.2(a): Schedule for Intervention and Instrument (KC-EP) for the Mothers' in Control and Experimental Groups**

Days/ Weeks	Control Group		Experimental Group		Person in charge
	Activities	Instrument	Activities	Instrument	
Admission Day	Routine NICU practice	Brief NICU orientation	Review (Medical Report)	Brief NICU orientation	Review (Medical Report)
Day 1 (PI: Week 28)					
Day 2		Breastfeeding Support, Hand Washing	KCQ (QI) & PSS: NICU:P&R KCPR Booklet	Simple ward orientation, First meeting	KCQs (QI) & PSS: NICU:P&R KCPR Booklet
Day 3		Breastfeeding Support + Attending mother whenever are approach by mother ad hoc		Short Message: WhatsApp (1)	Researcher
Day 4				Subsequent Meeting	Researcher
Day 5					
Day 6					
Day 7 (PI: Weeks 29)				Short Message: WhatsApp (2)	Researcher
Day 8					
Day 9					
Day 10 - Day 13					
Day 14 (PI: Week 30)				Short Message: WhatsApp (3)	Researcher

PI=Premature Infant; NICU=Neonatal Intensive Care Unit; KCRP Booklet=Kangaroo Care Progress Record Booklet;

**Table 3.2(b): Schedule for Intervention and Instrument (KC-EP) for the Mothers' in Control and Experimental Groups (Continued)**

Days/ Weeks/ Months	Control Group		Experimental Group		Person in charge
	Activities	Instrument	Activities	Instrument	
PI: Week 32	Routine NICU practice	Breastfeeding Support + Attending mother whenever are approach by mother ad hoc	Short Message: WhatsApp (4)		Researcher
PI: Week 34			Short Message: WhatsApp (5)		Researcher
PI: Week 36			Short Message: WhatsApp (6)		Researcher
PI: Week 38			Short Message: WhatsApp (7)		Researcher
PI: Week 40			Telephone Follow- up (1)		Researcher
PI: Week 44 (1st month)		KCQs & PSS: NICU:P&R (QI)	Short Message: WhatsApp (8)	KCQs & PSS: NICU:P&R (QI)	Researcher
PI: Week 48 (2nd months)			Telephone Follow- up (2)		
PI: Week 52 (3rd months)		KCQs & PSS: NICU:P&R (QI)	Short Message: WhatsApp (9)	KCQs & PSS: NICU:P&R (QI)	Researcher
			Telephone Follow- up (3)		

*PI= Premature Infant; NICU=Neonatal Intensive Care Unit; KCQ=Kangaroo care questionnaire; PSS: NICU=Parental Stress Scale: Neonatal Intensive Care Unit.*

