**i) Contents Module Theory and Practical (8 hour)**

Module contents were organized to meet the objectives of this study. Purposes included the definition of KC, method of KC, benefits of KC, indication and contraindication of KC, guidelines and protocol for KC, recognized signs and symptoms of deterioration during and after the KC procedure, preparation of premature infant-mothers and equipment before, during and after the KC procedure, and showing how to record the infants' outcomes data for both groups in the KCPR booklet provided. The nurse should have been able to get a clear understanding of the programme and of the physiology and benefits of KC in detail and demonstrate the technique as well [Appendix P, Q(a)& Q(b)].

- 1) To define the term and amount of KC.
- 2) To explain the physiology and method of KC.
- 3) To state the benefits of KC to mother-infant dyads.
- 4) To state the indication and contraindication for kangaroo care and eligibility criteria for mothers and premature infants.
- 5) To state the guidelines and protocols before, during, and after the kangaroo care method.
- 6) To recognize signs and symptoms of deterioration among premature infants before, during , and after the method.
- 7) To state the preparation before, during and after the kangaroo care method
- 8) To list the equipment for kangaroo care method ;
  - 8.1 For infants
  - 8.2 For mothers
- 9) To educate and guide on recording in the KCPR booklet.
- 10) To demonstrate and return-demonstrate the KC method.

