The control group mothers came for visits and saw their preterm infants once a day for 30 minutes to 1 hour, and exercised KC if they were interested. This was the NICU's routine practice. The control group of mothers continued routine ward practice and standard hospital care. Mothers who declined to participate during the time of the study were excluded. For participation in the study, a small token gift was given to (n=48) mother-infant dyads at the control group.

Upon their premature infant's discharge from the hospital, the mothers were reminded to answer the same standardized questionnaire (QI) for T0, T1, and T2. The following posttest questionnaires (Questionnaire I: enclosed in the envelope) were given to the mothers at the NICU or the Pediatrics Clinic on the 1st and 3rd month, when they came for their premature infant's follow-up, and were returned the same day. Consequently, some of the data were collected and sent by email if the mothers could not keep to the time (received on the same day).

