categorical variables are both independent and dependent variables. Therefore, covariance analysis was used to correct the observed effects on the outcome variables of potential confounders. The summary of the statistical analysis used for all research questions is outlined in Table 3.14. Each of the statistical tests is two-tailed. A p-value below 0.05 was assumed to show statistical significance.

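### Feeding status, and to a lesser extent weight at 1 and 3 months, is prompted by the researcher in the experimental arm but rests on a self-kept booklet in the control arm, so ascertainment can differ by arm

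*Combined protocol and SAP*

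**What the plan says.** Weight gain and length of stay (LOS) are primary outcomes and breastfeeding is secondary (Section 3.9 b).

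**Experimental arm.** Section 3.14.5 describes WhatsApp reminders asking mothers for updates that include "body weight of preterm infant on discharge, at 1 month and 3 months corrected age, breastfeeding status every 2 weeks post-admission". The feeding request runs to week 40 and continues at weeks 44, 48 and 52. Table 3.2(a) and (b) places nine numbered messages and three calls in the experimental column; the text of Section 3.13 says ten messages. At the first meeting the researcher goes through the Kangaroo Care Progress Record (KCPR) booklet with the mother and later sends reminders about it (Section 3.14.2). Section 3.16.2, on this arm, lets a relative keep the record at home.

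**Control arm.** Table 3.2 gives routine practice, "Breastfeeding Support + Attending mother whenever are approach by mother ad hoc", and questionnaires at weeks 44 and 52. Section 3.16.1 gives mothers a booklet to fill in until 3 months, with no kangaroo care (KC) input. Questionnaires are handed over at the 1- and 3-month visits, "when they came for their premature infant's follow-up, and were returned the same day", or emailed if the mother cannot keep the time.

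**Recording instruction.** The nurses' module includes "showing how to record the infants' outcomes data for both groups in the KCPR booklet provided" (Section 3.15, module contents). Section 3.16 dates the nurse phase August to September 2018 and control data collection February to July 2018.

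**The concern.** In the experimental arm one contact does two jobs: it encourages KC and breastfeeding, and it asks for the outcome. Controls get neither. Feeding status is self-reported, so experimental mothers are asked for it repeatedly by the person who teaches them to breastfeed, while control mothers write it down unasked or not at all. A difference in reported feeding could then reflect the programme, more complete records, or more favourable answers, and the plan offers no way to tell these apart. The same applies, less strongly, to weight at T1 (1 month) and T2 (3 months), which Section 3.16.4 says is recorded in the booklet. Section 3.19.1 states no method for missing data.

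**Working it through.** **1. The plan's own sample size, to see whether lost data is a power problem.** Inputs from Section 3.7.2: difference 0.54, SD 0.8, z-values 1.96 and 0.842. The origin of the 0.54 is a separate question. From Section 3.19.1: "Each of the statistical tests is two-tailed" and "A p-value below 0.05 was assumed to show statistical significance".

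- n = 2 × (1.96 + 0.842)² × 0.8² / 0.54² = 10.05 / 0.2916 = 34.46, so 35 per group. The plan shows 34.65 because it rounds 0.2916 to 0.29.
- 35 / (1 − 0.30) = 50 per group. Both stated figures reproduce.
- Power with 48 per arm: 0.54 / (0.8 × √(2/48)) − 1.96 = 1.35, which gives 91%.
- With 48 experimental infants and control completeness of 90% to 60% (assumed), power is 90% to 82%.

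Loss of control records alone costs little power. The issue is bias.

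**2. What is asked, and when.**

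| | Experimental | Control |
|---|---|---|
| Feeding status | Requested every 2 weeks to week 40, then weeks 44, 48, 52 | Booklet; no prompt stated |
| T1 and T2 weight | Requested at 1 and 3 months | Booklet; no prompt stated |
| Booklet explained by researcher | Yes, with reminders | Not stated; no KC input |
| Questionnaire at weeks 44 and 52 | Yes | Yes |
| Discharge weight and date | Senior nurse (Section 3.14.5) | No separate route stated; Section 3.16.4 gives common in-hospital recording |

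**3. Scheduled contacts.** Table 3.2 gives 9 + 3 = 12 numbered contacts in the experimental arm and none in the control arm. Many fall in hospital. If discharge is at 34 weeks (assumed), those left are messages at weeks 36, 38, 44 and 52 and calls at weeks 40, 48 and 52: 4 + 3 = 7. If it is at 38 weeks, 2 + 3 = 5 are left.

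**4. Timing of the nurse instruction.** T2 is at week 52. From recruitment at 28 weeks this is 24 weeks away; from 36 weeks 6 days it is 15 weeks 1 day. To reach T2 by 31 July 2018 a control had to be recruited by 13 February or 16 April respectively. A control recruited on 31 July, the stated end of selection, reaches T2 between 14 November 2018 and 15 January 2019. So the instruction comes after control data collection on the stated dates, but later control follow-up would run past it.

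**5. Illustration only.** Suppose the true feeding rate p is the same in both arms (30% to 60%), experimental data are complete, and 10% to 30% of control entries are missing and counted as not breastfeeding. The false difference is p × missing fraction: 0.30 × 0.10 = 3 points up to 0.60 × 0.30 = 18 points. With 48 per arm, the normal approximation gives a chance of p < 0.05 favouring the programme of about 5% to 42%, against 2.5% without bias. The plan states no such counting rule. If missing entries are left out and are unrelated to feeding, this false difference is zero.

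**The case against.** The best reply is that the plan does set common methods. Section 3.16.4 describes one weighing procedure under hospital protocol, one booklet for either group, and data from both groups at T0, T1 and T2. It gives the messages' purpose as continuity of care, and nowhere says that a WhatsApp value replaces a booklet value. Controls are seen at both follow-up points. Section 3.16.4 also mentions calls and WhatsApp without naming an arm, straight after a sentence about both groups.

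Part of this stands. A reader might infer that weight is prompted every 2 to 4 weeks in one arm. It is not: weight is requested only at discharge, 1 month and 3 months, and the 2-week interval belongs to feeding status. A reader might also infer that in-hospital control records were made by untrained staff. The documents do not show that. Weighing followed existing protocol, the control booklet was piloted beforehand (Section 3.20.1), and NICU nurses who checked the booklet could understand it (Section 3.14.3).

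The rest does not remove the gap. The control visits are described only for the questionnaire. The common weighing procedure is a hospital one, and no text says who weighs the infant at T1 and T2. The unassigned sentence on calls is followed by one limiting the chat group to the experimental arm, and Table 3.2 agrees. It needs clarifying, but it does not establish a control prompt.

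**Conclusion.** The concern holds in a limited form. As written, the plan allows ascertainment to differ by arm for feeding status after discharge and, to a lesser extent, for T1 and T2 weight. Discharge weight and LOS are little affected. Self-reports to the researcher who promotes breastfeeding may favour the programme; for weight, the documents show no direction.

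The size cannot be derived. The 5 to 7 post-discharge contacts assume discharge at 34 to 38 weeks. The 3 to 18 point range assumes a counting rule that the plan does not contain, so it shows what could happen and is not an estimate. The 30% allowance in Section 3.7.2 is a general one for missing values and non-response, and should not be read as a control booklet loss rate. The late nurse instruction is a secondary weakness, because part of the control follow-up would come after it.

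**What to change.** - Record T1 and T2 weight and feeding status in both arms at the existing 1- and 3-month follow-up, on one form with one feeding question. Where a mother cannot attend, use email, as Section 3.16.1 already allows for some data.
- Do not use WhatsApp-reported weight or feeding as outcomes unless the same data-only prompt, free of KC or breastfeeding advice, goes to controls in the same weeks.
- State in Section 3.16.4 which arm the calls and WhatsApp conversations concern.
- Report completeness of weight and feeding data by arm and time point, and do not count missing feeding data as not breastfeeding.
- Give nurses a recording-only instruction before the first control is enrolled. It must carry no KC content, so that their KC pretest (Section 3.17) is not affected.

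The cost is one short form, a brief recording session and, if chosen, a neutral message to controls. There are two downsides: slightly more contact with control mothers may prompt feeding a little, and interim feeding data are lost as an outcome if controls are not prompted.
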